Epilepsy surgery involves resecting epileptogenic tissues including limbic structures which may be functionally normal. Hence the emergence process can be complicated in patients having diseased limbic structures or those having therapeutic removal of limbic structures as in epilepsy surgery. Limbic structures are responsible for memory, language and executive function and hence loss of some of these higher functions is to be expected in the postoperative period. Preoperative neuropsychological assessments are often used to predict their risk for postoperative loss of higher functions and behavior changes. In our experience the investigators have seen that there is a spectrum of emergence characteristics in patients undergoing temporal lobectomy that can vary from dangerously agitated patient to much sedated, unarousable patient. Delirium and agitation can be dangerous and have serious consequences for the patient such as injury, increased pain, hemorrhage, self-extubation and removal of catheters requiring physical or chemical restraint. On the other hand, the unarousable patient may pose dangerous airway complications and limit neurological assessment in the immediate postoperative period. Hence it is essential to have a clue about post anesthesia emergence behavior in patients having epilepsy

surgeries. The aim of this study is to look at the pattern of emergence from anesthesia after epilepsy surgery and to determine if preoperative neuropsychological assessment help predict the pattern of emergence in patients undergoing anterior temporal lobectomy and amygdalohippocampectomy.

Background

Emergence from anesthesia starts with activation of deep brain structures namely subcortical and limbic regions of the brain. Later they become functionally coupled with other parts of brain including frontal and inferior parietal cortex. Arousal (spoken command) induced brain activations during emergence from anesthesia are mostly localized in deep, phylogenetically old brain structures (limbic cortex or mesial temporal structures) than in neocortex.¹

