Physiologically, when emerging from deep anesthesia there will first be signs of autonomic arousal, followed by a slow return of brainstem reflexes, eventually leading to reflexive or uncoordinated movements that occur somewhat before subjects can willfully respond to simple commands. Thus, emergence of a conscious state, precedes the full recovery of neocortical processing required for establishing contact with the surroundings. The prevalence of epilepsy is around 0.4–0.8%² and 20–30% of these patients will develop medically refractory seizures²⁻⁴ and hence present for surgical treatment.

Epilepsy surgery involves resecting epileptogenic tissues including limbic structures which may be functionally normal. Anterior temporal lobectomy and amygdalohippocampectomy is a well-established surgical treatment for the patients with temporal lobe epilepsy and these parts of the brain have a role in the emergence from general anesthesia. Due to asymmetry of temporal neocortical (dominant vs nondominant) and mesial temporal functional representations, the loss of these structures and hence their functions in the postoperative period complicates emergence from anesthesia in these patients³. Preoperative neuropsychological assessments are often used to predict the risk for postoperative loss of higher functions and behavior changes.

Rationale

There are no study related interventions in this study and perioperative care of these patients will be as per our standard practice. The only study related protocol would be collecting the data on the emergence from anesthesia. The data will be collected from the time of turning off the anesthetic agents till the discharge from recovery room. Data collected include, vital signs, Glasgow coma scale (GCS), and Riker agitation- sedation score. The patients will be assessed every 5 minutes for the first 30 minutes and every 10 minutes for the next 60 minutes.

Study Objective and Hypothesis

The aim of this study was to look at the pattern of emergence from anesthesia after epilepsy surgery and to determine if preoperative neuropsychological assessment help predict the quality of emergence in patients undergoing anterior temporal lobectomy (ATL) and amygdalohippocampectomy (AH).

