Data will be collected from the time of turning off the anesthetic agents till the discharge from recovery room. Patients will be assessed every 5 minutes for the first 30 minutes and every 10 minutes for the next 60 minutes. Data collected will include patient demographics, preoperative neuropsychological assessment data, Age, Intelligence quotient (IQ), Verbal, visual, language memory, education, History of psychiatric illness, Dexterity of the patient and side of surgery, Time of emergence from anesthesia, Vital signs, Glasgow Coma Scale (GCS) score, and Riker agitation score (7-agitated;dangerous agitation, 6-very agitated, 5-agitated, 4-nonagitated;calm and cooperative, 3-sedated but arousable, 2-very sedated, 1-unarousable).

Data Analysis

There are no previous studies looking at the emergence characteristics in patients with temporal lobectomy. As this is an observational study, there are no cause effect relationship to calculate sample size. Emergence characteristics were classified as either smooth emergence (Riker scale 3-4) or agitated emergence (Riker scale >4). Correlation coefficients will be used to compare the data between preoperative neuropsychological scores and the emergence characteristics (smooth vs. agitated) and the time of emergence. Quantitative variables like hemodynamics will be analyzed using student's t-test. Qualitative variables like sex distribution will be analyzed using Chi-square test. A p-value less than 0.05 is considered significant.

CONCLUSION

Smooth emergence (wake up) from anesthesia is an important consideration in patients undergoing neurosurgical procedures as blood pressure changes associated with violent emergence can cause intracranial hemorrhage and brain swelling. At the same time, emergence should also be quick so that patients' neurological function can be assessed at a timely manner. Pattern of emergence from anesthesia is poorly investigated and understood.

REFERENCES

1. Jaakko W. Långsjo, Michael T. Alkire, et al. Returning from Oblivion: Imaging the Neural Core of Consciousness. The Journal of Neuroscience. 2012; 32:4935– 4943
3. Gilliam F. The impact of epilepsy on subjective health status. Curr Neurol Neurosci Rep 2003; 3:357–62

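### The plan states no way to capture agitation, or treatment given for it, between scheduled Riker checks, so a short or promptly treated episode may leave no score above 4

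*Combined protocol and SAP*

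**What the plan says.** Rationale and Data Collection give the same schedule, in Data Collection as "Patients will be assessed every 5 minutes for the first 30 minutes and every 10 minutes for the next 60 minutes". That makes 12 scheduled checks, or 13 if time zero is also scored. The collection window is wider: "Data will be collected from the time of turning off the anesthetic agents till the discharge from recovery room". No schedule is given after 90 minutes.

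The recovery-period items named in Data Collection are "Time of emergence from anesthesia, Vital signs, Glasgow Coma Scale (GCS) score, and Riker agitation score". Agitation events between checks, restraint and sedatives given for agitation are not among them.

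Data Analysis defines the outcome: "Emergence characteristics were classified as either smooth emergence (Riker scale 3-4) or agitated emergence (Riker scale >4"). It does not say how a dozen repeated scores become one class, and Riker 1-2 belongs to neither class. The class is then correlated with the preoperative neuropsychological scores.

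Two further statements bear on the point. The introductory text before Background lists, among the consequences of agitation, "self-extubation and removal of catheters requiring physical or chemical restraint". Rationale says "There are no study related interventions in this study and perioperative care of these patients will be as per our standard practice".

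**The concern.** The class depends on whether a score above 4 is on record. If Riker is read as the patient's state at the moment of each check, an episode that begins and ends between two checks produces no such score. The plan itself expects that agitation may be restrained or sedated, and since care follows standard practice, treatment would not wait for the next check.

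Choosing the peak of the scheduled scores does not solve this, because the peak was never scored.

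At stake are both aims in Study Objective and Hypothesis. The description of emergence would omit some agitated patients, and the analysis of prediction would use an outcome with imperfect sensitivity. The plan sets no sample size, so nothing in it allows for lost precision.

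**Working it through.** The plan states no figure on this point, so there is none to reproduce.

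**Inputs from the documents.** Intervals of 5 minutes (0-30) and 10 minutes (30-90), from Data Collection; agitated means Riker above 4, from Data Analysis.

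**Assumptions.** Riker is scored as an instantaneous state; there is one episode of length d minutes, timed at random; the schedule is kept. The documents give neither d nor the true proportion agitated.

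**Step 1: chance that one episode is missed.** On a grid of width w, an episode is missed if it lies wholly between two checks, with probability max(0, 1 - d/w).

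| d (min) | 5-minute grid | 10-minute grid |
|---|---|---|
| 1 | 1 - 1/5 = 80% | 1 - 1/10 = 90% |
| 2 | 60% | 80% |
| 3 | 40% | 70% |
| 4 | 20% | 60% |
| 5 | 0% | 50% |
| 10 | 0% | 0% |

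If onset is uniform over the whole 90 minutes, the start times that lead to a miss total 6(5 - d) + 6(10 - d) = 90 - 12d minutes (for d up to 5), out of 90 - d possible. This gives 78/89 = 88% for 1 minute, 66/88 = 75% for 2, 54/87 = 62% for 3 and 30/85 = 35% for 5. If agitation clusters early, the 5-minute column applies.

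**Step 2: repeated episodes.** A patient is missed only if every episode is missed. With three independent 2-minute episodes on the 5-minute grid, the chance is 0.6³ = 22%, against 60% for one episode. Single-episode figures are therefore not patient-level sensitivities.

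**Step 3: effect on a correlation.** Let p be the true proportion agitated and s the proportion of agitated patients detected. Assume no false positives and misses unrelated to the preoperative scores. The correlation is then multiplied by √[s(1 - p)/(1 - sp)]. With p = 0.25, chosen only for illustration:

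- s = 0.8: √(0.60/0.80) = 0.87; recorded agitation 20%
- s = 0.6: √(0.45/0.85) = 0.73; recorded agitation 15%
- s = 0.4: √(0.30/0.90) = 0.58; recorded agitation 10%

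The squared multipliers, 0.75, 0.53 and 0.33, are the approximate effective sample size as a fraction of the patients enrolled. At s = 0.6 the multiplier runs from 0.76 (p = 0.10) to 0.65 (p = 0.50). At s = 1, where every episode lasts at least as long as the interval, nothing is lost.

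**Step 4: the opposite error.** Background describes reflex, uncoordinated movement as a normal stage before patients respond to commands. If an interval-peak score picks this up as agitation, specificity falls. With p = 0.25, perfect sensitivity and specificity c, the recorded proportion is q = 0.25 + 0.75(1 - c) and the multiplier is c√(0.1875)/√[q(1 - q)]. For c = 0.9, q = 0.325 and the multiplier is 0.83; for c = 0.8, q = 0.40 and it is 0.71. These losses are similar to those at s = 0.8 and s = 0.6, so the fix must guard against over-classification.

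**The case against.** The strongest reply is that the schedule is a reasonable design choice and that the gap is read from silence. Nothing says Riker is scored at those times alone or bars an unscheduled score. Collection runs until recovery room discharge, the list of items is introduced as what the data will include, and no case report form is in the documents. Staff may note such episodes in practice. This stands as a limit on the claim: a reader might infer that between-check scoring is ruled out, and the documents do not say so. But they do not provide for it either, and unwritten practice can vary between assessors.

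Three further objections stand.

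- A reader might infer that the most severe episodes are the likeliest to be missed, because they are treated at once. That is conjecture. The text says agitation may need restraint, not that it then ends within 5 minutes. Severe episodes could last longer, and physical restraint need not bring the score down.
- A reader might infer that every missed patient is counted as smooth. That requires later scores of 3-4. A patient just sedated may score 1-2, which is in neither class; either way the patient is lost from the agitated group.
- The missing rule for combining repeated scores is the more basic gap. Without an any-score or peak rule, even agitation that was scored could be classed as smooth. The present point remains once that rule is supplied, because no rule can use a score that was never taken.

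**Conclusion.** The point holds as a cheap improvement to measurement, not as an error that invalidates the design. Followed as written, the plan can leave a short or promptly treated episode without a score above 4.

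Its size cannot be computed from the documents. The 80% to 20% and 90% to 60% miss probabilities rest on a single, randomly timed episode of 1 to 4 minutes and an instantaneous score. At 5 minutes or more the miss probability is zero on the 5-minute grid if the schedule is kept, and repeated episodes lower it further. The correlation multipliers rest in addition on an assumed prevalence, assumed sensitivity and perfect specificity, so they show scale and do not predict this study's loss.

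A reader might also infer that the association is bound to be weakened. Bias toward zero follows only if misses are unrelated to the preoperative scores. If prompt treatment depends on something linked to those scores, for example a known psychiatric history, the direction is unpredictable. Nor is the frequency of agitation named as a quantity to be estimated; the stated aim is the pattern of emergence, of which frequency is a natural part.

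**What to change.** Change the recording and the classification rule; schedule, assessor and care stay as they are.

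- At each scheduled check, record the current Riker score and the highest score since the previous check. For the first check, the interval starts when the anesthetic agents are turned off.
- Log any restraint or sedative given for agitation, with its time.
- In Data Analysis, class a patient as agitated if any current or interval score exceeds 4, or if restraint or sedation was given for agitation.
- Report the classification from scheduled scores alone as a sensitivity analysis.
- Instruct assessors on the form not to score brief reflexive emergence movements as agitation.

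The cost is one extra column and a short treatment log on the existing form. There are two downsides. The interval score relies on observer recall over 5 to 10 minutes, and some normal emergence movement may still be labelled agitation despite the instruction. The sensitivity analysis shows how far the results depend on the between-check information.

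### The planned correlation reduces the seven-level Riker score to smooth (3-4) versus agitated (>4), so agitation severity already recorded goes unused; the likely statistical gain from keeping it is modest

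*Combined protocol and SAP*

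**What the plan says.** Data Collection lists the Riker score with all its levels: "7-agitated;dangerous agitation, 6-very agitated, 5-agitated, 4-nonagitated;calm and cooperative, 3-sedated but arousable, 2-very sedated, 1-unarousable". It is read repeatedly: "Patients will be assessed every 5 minutes for the first 30 minutes and every 10 minutes for the next 60 minutes". That is 30/5 + 60/10 = 6 + 6 = 12 scheduled readings.

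Data Analysis then defines two classes: "Emergence characteristics were classified as either smooth emergence (Riker scale 3-4) or agitated emergence (Riker scale >4"). The only analysis that links these to the predictors is: "Correlation coefficients will be used to compare the data between preoperative neuropsychological scores and the emergence characteristics (smooth vs. agitated) and the time of emergence". No ordinal, peak-score or duration analysis of the Riker score is planned.

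Study Objective and Hypothesis gives the aim as describing the pattern of emergence and "to determine if preoperative neuropsychological assessment help predict the quality of emergence". The introductory text, before Background, says that emergence after temporal lobectomy "can vary from dangerously agitated patient to much sedated, unarousable patient".

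**The concern.** The motivation for the study lies at the two ends of the scale. The introductory text ties agitation to injury, hemorrhage and self-extubation, and says of the other end that "the unarousable patient may pose dangerous airway complications and limit neurological assessment in the immediate postoperative period". The analysed outcome separates neither end from its neighbours. A patient at 5 and a patient at 7 receive the same value, and so do a patient at 3 and a patient at 4. Levels 1 and 2 receive no value.

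Two things are at stake. First, cutting an ordered score at one point weakens any true association with the neuropsychological scores. Second, the planned analysis does not show whether those scores track the severity of agitation, and the plan does not commit the report to showing how many patients reached 6 or 7. Time of emergence is analysed separately, but it measures speed and does not restore severity.

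**Working it through.** The plan states no sample size, power, effect size or Riker distribution, so there is no figure to reproduce. The size of the loss is illustrated under assumptions.

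**Mapping (from Data Analysis).** Levels 3 and 4 become smooth; levels 5, 6 and 7 become agitated; levels 1 and 2 become neither. Five ordered levels are reduced to two, and two are left out.

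**Model (assumed).** A normal latent agitation trait lies behind each patient's peak score. For each way of scoring, compute the fraction of the latent correlation that is retained. For small correlations, the number of patients needed is roughly proportional to 1/(fraction squared), so the ratio of squared fractions approximates the gain in information.

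**Binary cut**, with proportion p agitated and z the upper-p normal point: fraction = φ(z)/√(p(1−p)).

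- p = 0.30: 0.3477/0.4583 = 0.759, squared 0.576
- p = 0.20: 0.2800/0.4000 = 0.700, squared 0.490
- p = 0.10: 0.1755/0.3000 = 0.585, squared 0.342

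**Ordinal score.** Level k has share p_k and mid-rank s_k (cumulative share below, plus p_k/2). Let d_k = φ(lower cut) − φ(upper cut). Then fraction = Σ s_k d_k / √(Σ p_k s_k² − 0.25).

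Worked case, 70/18/8/4% at levels 4/5/6/7:

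- s = 0.35, 0.79, 0.92, 0.98
- d = −0.3477, 0.1477, 0.1139, 0.0862
- Σ s_k d_k = 0.1842; variance = 0.0542
- fraction = 0.1842/√0.0542 = 0.791, squared 0.626

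| Assumed peak scores | Agitated | Binary, squared | Ordinal, squared | Gain |
|---|---|---|---|---|
| 70/18/8/4% at 4/5/6/7 | 30% | 0.576 | 0.626 | about 9% |
| 80/12/5/3% at 4/5/6/7 | 20% | 0.490 | 0.513 | about 5% |
| 90/6/3/1% at 4/5/6/7 | 10% | 0.342 | 0.348 | about 2% |
| 20/50/18/8/4% at 3/4/5/6/7 | 30% | 0.576 | 0.853 | about 48% |

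**Where the 48% comes from.** In the last row, separating only 3 from 4 and leaving 5-7 merged (20/50/30%) already gives 0.803, and 0.803/0.576 = 1.39. Separating 5, 6 and 7 as well adds 0.853/0.803 = 1.06. So about 39% comes from the split of 3 from 4, and a further 6% from agitation severity.

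**Sensitivity.** If half the patients were agitated (50/25/15/10% at 4/5/6/7), the gain would be about 22% with nobody peaking at 3. The 2% to 9% range therefore applies to 10% to 30% agitated.

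**A second illustration.** A simulation that spread patients over levels 3-7, with 15% to 30% at level 3 and 15% to 60% agitated, found that the binary outcome needs about 1.35 to 1.85 times as many patients for 80% power. It agrees in direction. It does not model the peak score, so it does not measure the gain from the fix below.

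**The case against.** The strongest reply is that the two-class outcome is a legitimate simplification. The cut between 4 and 5 follows the scale's own labels, nonagitated against agitated, and matches the Conclusion's contrast of smooth with violent emergence. On the figures above, separating 5, 6 and 7 gains only 2% to 9% when smooth patients peak at 4. The large figure needs 20% of patients never to reach 4 at any reading. That is a strong assumption: Standard perioperative management requires patients to obey commands before extubation, and readings continue until recovery-room discharge. This part of the reply stands, and it limits the size of the point.

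The peak score also has limits. A patient who stays at 3 for most of recovery and then reaches 4 ranks the same as one who was calm throughout. The Riker scale runs both ways from calm, so a one-directional correlation describes agitation level, not overall quality of emergence. This stands too, and the fix allows for it.

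A reader might infer that the cut prevents the study from saying anything about dangerous agitation. The documents do not support that: all seven levels are recorded and can still be tabulated. Nor would a Spearman coefficient isolate level 7. At an assumed 4% of an illustrative 40 patients, 40 × 0.04 = 1.6 patients would be there. A reader might also take the cohort to be small, or level 5 to be mild agitation. No sample size is stated, and the documents label level 5 simply as agitated.

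The reply does not remove the mismatch itself. The planned correlation uses less of the recorded scale than the aim calls for, and no other planned analysis makes up for it.

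**Conclusion.** The point stands in modest form. The reading of the plan is certain: one binary cut is the only Riker outcome that is correlated with the neuropsychological scores, and levels 1-2 fall outside it. This is a loss of information and of fit to the aim; it is not an arithmetic error.

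The size is uncertain. The gain from keeping the peak score ordinal is about 2% to 9% in squared correlation with 10% to 30% agitated and all smooth patients peaking at 4. With 30% agitated it rises to about 48% if 20% never exceed 3. All of this rests on a normal latent trait and on assumed category shares. It would be wrong to present the 48%, or the 35% to 85% larger sample from the simulation, as the expected benefit. The firmer reason to change is that a peak-score analysis and table address severity directly, using data already planned.

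**What to change.** In Data Analysis:

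1. Make the main Riker outcome each patient's highest score over the observation period, kept on its ordinal scale, and relate it to the neuropsychological scores by Spearman correlation. Describe it as agitation level.
2. Keep smooth (3-4) versus agitated (>4) as a secondary summary, classed from the same highest score.
3. Tabulate the number of patients at each peak score, so that levels 6 and 7 are visible.
4. Report levels 1-2 separately, for example by each patient's lowest score after extubation. Peak score does not capture the sedated end. Starting after extubation avoids counting readings taken before the patient has woken, since collection begins when the anesthetic agents are turned off.

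The cost is a few sentences and no new data. Correlation coefficients are already the planned method, so the type of analysis does not change. The downside is that the headline becomes a rank correlation instead of a two-group contrast, and the statistical gain may be modest.

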We hypothesized that there will be a relationship between preoperative neuropsychological assessment scores and the limbic structure (hippocampus, amygdala and thalamus) volumes with the quality of emergence from anesthesia in patients undergoing anterior temporal lobectomy and amygdalohippocampectomy.

Study Design

This prospective, observational study will be conducted after approval from institutional ethics board and written informed consent will be obtained from each subject.

Eligibility Criteria

Inclusion Criteria:

- Adult patients above the age of 18 who are scheduled for elective anterior temporal lobectomy and amygdalohippocampectomy under General Anesthesia

Exclusion Criteria:

- Lack of informed consent
- Patients needing intensive care unit postoperatively

Study Procedure

Standard perioperative management

Anesthesia and neurosurgical care of the patients is as per the standard institutional practice. Preoperatively all patients will be seen by the anesthesiologists in the pre-anesthesia consult clinic.

Intraoperatively, all patients will have standard monitoring consisting of electrocardiography (ECG), pulse oximetry, end-tidal carbon dioxide (ETCO₂), invasive and non-invasive blood pressure, temperature, urine output, depth of anesthesia (Entropy) and end tidal anesthetic agent concentration.

Anesthesia induction will be with propofol (1-2 mg/kg), fentanyl (2-3mcg/kg) and rocuronium (0.8-1.2mg/kg).

Anesthesia will be maintained with oxygen, air, sevoflurane (0.8-1 MAC (Minimal Alveolar Concentration)) and remifentanyl infusion titrated to keep entropy within 45-55.

After induction and positioning, the surgery (ATL and/or AH) will be proceeded as per standard. After dural closure, inhalational agent concentration will be decreased gradually to MAC of 0.6 and fentanyl 1-2mcg/kg administered for additional analgesia.

After the closure of scalp, inhalational agent will be turned off.

Remifentanyl infusion will be turned off once the head is disengaged from head pins and after completion of the head dressing.

The patients will be allowed to wake up with “no touch technique”.

Extubation will be done when the patients are breathing adequately, spontaneously and obeying commands.

Post-surgery, patients recovered in the post anesthesia care unit (PACU) before being discharged to the neurosurgical critical care unit.

Data Collection

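### The emergence rule has no class for patients who stay very sedated or unarousable (Riker 1-2), so one of the two dangers the study names is not counted in its emergence outcome

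*Combined protocol and SAP*

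**What the plan says.** The opening summary of the combined protocol and SAP reports the investigators' experience that "there is a spectrum of emergence characteristics in patients undergoing temporal lobectomy that can vary from dangerously agitated patient to much sedated, unarousable patient". It treats both ends as hazardous. Of the sedated end it says that "the unarousable patient may pose dangerous airway complications and limit neurological assessment in the immediate postoperative period". Under Study Objective and Hypothesis, "The aim of this study was to look at the pattern of emergence from anesthesia after epilepsy surgery", and to see whether preoperative neuropsychological testing predicts its quality.

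The data cover the whole range. Rationale states: "Data collected include, vital signs, Glasgow coma scale (GCS), and Riker agitation- sedation score". Data Collection lists all seven Riker levels, the lowest two being very sedated (2) and unarousable (1). Readings are scheduled every 5 minutes for 30 minutes, then every 10 minutes for a further 60.

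Data Analysis reduces this to two classes: "Emergence characteristics were classified as either smooth emergence (Riker scale 3-4) or agitated emergence (Riker scale >4". The preoperative scores are then correlated with smooth versus agitated and with time of emergence.

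**The concern.** The rule gives no class to the levels that describe one of the two dangers motivating the study, and no other section says what happens to patients at those levels. Followed as written, the plan reports how often emergence was agitated but not how often patients stayed deeply sedated. Whoever runs the analysis must decide, with the data in view, whether to drop such patients, call them smooth or leave them as a remainder. The first two choices make emergence look smoother than it was. The aim is the pattern of emergence, and that pattern would have an outcome class at only one of its two dangerous ends.

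**Working it through.** The plan states no sample size, rate or effect, so there is no figure of its own to reproduce.

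**Step 1: apply the rule to each level.** Riker 1: no class. 2: no class. 3 and 4: smooth. 5, 6 and 7: agitated. Two of seven levels are unclassified.

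**Step 2: effect on the reported smooth share.** Let *a* be the agitated share and *s* the share at Riker 1-2, both out of all assessed patients. Both values are assumptions: *a* = 20%; *s* = 5%, 10% or 20%.

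- True smooth share = 1 - a - s
- Sedated dropped from the denominator = (1 - a - s)/(1 - s)
- Sedated folded into smooth = 1 - a
- All patients kept in the denominator, sedated left unlabelled = 1 - a - s, which is correct but leaves *s* as an unexplained remainder

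| s | True | Dropped | Folded in |
|---|---|---|---|
| 5% | 75% | 0.75/0.95 = 78.9% | 80% |
| 10% | 70% | 0.70/0.90 = 77.8% | 80% |
| 20% | 60% | 0.60/0.80 = 75.0% | 80% |

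Dropping also raises the agitated share, a/(1 - s), from 20% to 21.1%, 22.2% or 25.0%.

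The table treats Riker 1-2 as a fixed state of the patient. The plan has 30/5 + 60/10 = 12 scheduled readings and does not say which one sets the class, so a patient at 1-2 early may later score 3-4 or above 4.

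**Step 3: why a reading time is needed.** Data collection starts when the agents go off, while patients are still anaesthetised. The two agents need not stop together: "After the closure of scalp, inhalational agent will be turned off", whereas "Remifentanyl infusion will be turned off once the head is disengaged from head pins and after completion of the head dressing". Counting any early Riker 1-2 reading as sedated emergence would therefore capture ordinary awakening.

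**Step 4: what counting would give.** Exact (Clopper-Pearson) 95% intervals for assumed sample sizes of 40, 60 and 100:

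- 10% sedated: 4/40 = 2.8-23.7%; 6/60 = 3.8-20.5%; 10/100 = 4.9-17.6%
- 20% sedated: 8/40 = 9.1-35.6%; 12/60 = 10.8-32.3%; 20/100 = 12.7-29.2%
- None sedated: upper limits 8.8%, 6.0% and 3.6%

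**Step 5: relation to a preoperative score.** Assume 10% sedated, 70% smooth, 20% agitated and a within-class SD of 1.

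- *Score 0.8 SD lower in sedated patients only.* With the sedated dropped, the expected smooth/agitated coefficient is 0. Folded in, the mean of the smooth class is -0.8 × 0.10/0.80 = -0.10, so the coefficient is about 0.10 × √(0.8 × 0.2)/√(1 + 0.64 × 0.1 × 0.9) = 0.04. For sedated versus smooth, p = 0.10/0.80 = 0.125, giving 0.8 × √(0.125 × 0.875)/√(1 + 0.64 × 0.125 × 0.875) = 0.26.
- *Score tracking arousal evenly over the whole range (latent correlation 0.4).* By simulation, smooth/agitated gives 0.26 (dropped) or 0.28 (folded in), and sedated/smooth gives 0.22.

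In the first scenario at N = 60, with 6 sedated against 42 smooth, 95% of simulated sedated/smooth estimates lie between -0.02 and 0.50.

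**The case against.** The strongest reply is that the slow end already has an outcome. The scores are also correlated with time of emergence, and the Conclusion says emergence should be quick enough for timely neurological assessment. This stands in part. A reader might infer that sedated patients go wholly unexamined, but the documents do not support that: their Riker and GCS readings are kept, and a long time of emergence would partly reflect them. That time has no stated end point, however, and it does not classify or count patients who remain at Riker 1-2. GCS might fall under the general t-test provision for quantitative variables, but that would not count them either.

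A reader might also infer that the smooth share is overstated however these patients are handled. It is not: with all patients in the denominator and the sedated left unlabelled, it is correct. A patient with early low readings who later scores above 4 is agitated and does not inflate it.

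Sedated patients may also be few. "Extubation will be done when the patients are breathing adequately, spontaneously and obeying commands", and Eligibility Criteria exclude patients who need intensive care after surgery. That exclusion could remove the very patients who stay unarousable. How it operates is unclear, because Standard perioperative management also sends patients from recovery to a neurosurgical critical care unit. This does not remove the gap in the rule, but a proportion sedated, including a zero count, could be biased low and must be reported with that limit.

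Finally, every size shown above is assumed. The contrast of 0-0.04 against 0.26 needs a score that is lower only in sedated patients; in the even-tracking scenario the planned contrast does register the relation.

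**Conclusion.** The point holds in this form: Riker 1-2 has no class and no stated handling, so patients who remain very sedated or unarousable are not counted in the emergence outcome, although theirs is one of the two dangers that motivate the study. This is a defect in a stated rule, not merely missing detail. The smooth share is overstated if these patients are dropped from the denominator or folded into smooth. The documents do not allow the amount to be computed. Under the assumed 20% agitated and 5-20% sedated, the overstatement is about 4 to 15 percentage points if dropped (78.9 - 75 to 75 - 60) and 5 to 20 if folded in (80 - 75 to 80 - 60).

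It would go too far to conclude that a predictor of sedated emergence must be missed. That depends on how the score relates to arousal and on the undefined time of emergence. The smooth/agitated comparison remains usable, and the rule should be amended before analysis.

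**What to change.** In Data Analysis, replace the two-class rule with three classes and state the reading for each, timed from when the inhalational agent is turned off:

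- **Agitated:** any Riker above 4 during the scheduled assessments.
- **Sedated:** Riker 1-2 at the scheduled 30-minute assessment and never above 4.
- **Smooth:** all others.

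Keep all assessed patients in the denominator. Report:

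1. The number and proportion in each class with exact 95% intervals.
2. The count at Riker 1-2 at 90 minutes, as a sensitivity result, because remifentanil may stop after the inhalational agent.
3. The count of patients who meet both the sedated reading and the agitated criterion.
4. How many consented patients were excluded for postoperative intensive care and why, with a statement that the sedated proportion applies only to patients not so excluded.
5. As a secondary result, the correlation of each preoperative score with sedated versus smooth, as an estimate with a 95% interval, or counts only if fewer than 5 are sedated.

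The cost is a few sentences and a tally of exclusions; Riker is already recorded on this schedule. There are two downsides. The added category may be small (4 to 10 patients at N = 40-100 if 10% are sedated), so the proportion is the main result and at N = 40 the correlation would probably not be reported. The 30-minute cut-off is a choice not taken from the documents, and the plan should say so.
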